# 5.2 SERIOUS ADVERSE EVENTS

An AE should be classified as an SAE if the following criteria are met:

- It results in death (i.e., the AE actually causes or leads to death).
- It is life threatening (i.e., the AE, in the view of the investigator, places the subject at immediate risk of death. It does not include an AE that, had it occurred in a more severe form, might have caused death.).
- It requires or prolongs inpatient hospitalization.
- It results in persistent or significant disability/incapacity (i.e., the AE results in substantial disruption of the subject's ability to conduct normal life functions).
- It results in a congenital anomaly/birth defect in a neonate/infant born to a mother exposed to the IMP.
- It is considered a significant medical event by the investigator based on medical judgment (e.g., may jeopardize the subject or may require medical/surgical intervention to prevent one of the outcomes listed above).

# 5.3 METHODS AND TIMING FOR ASSESSING AND RECORDING SAFETY VARIABLES

The investigator is responsible for ensuring that all AEs and SAEs that are observed or reported during the study, are collected and reported to the FDA, appropriate IRB(s), and Genentech, Inc. in accordance with CFR 312.32 (IND Safety Reports).

# Adverse Event Reporting Period

The study period during which all AEs and SAEs must be reported begins after informed consent is obtained and initiation of study treatment and ends 30 days following the last administration of study treatment or study discontinuation/termination, whichever is earlier.

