#### b. Administration

Group 1 will undergo monthly intravitreal injections of 0.3 mg ranibizumab administered 30 days (+/- 7 days) following the last treatment for 12 months. Injections will be performed with sterile technique as outlined in appendix B.

Group 2 will be assigned to a "treat-and-extend" protocol. Eyes will be treated with 3 loading doses at 30-day (+/- 7 days) intervals. After the third loading dose, the follow-up interval is determined with an OCT-based protocol:

• **Criterion A:** If the central subfield thickness is less than or equal to 300 microns or there is complete absence of intraretinal or

subretinal fluid on the macular cube, the follow-up interval is increased by 2 weeks (+/- 7 days) at each visit [to a maximum interval of 12 weeks (+/- 7 days)]. The eye receives an intravitreal ranibizumab injection at every visit.

- Criterion B: If on subsequent follow-up visits, the thickness increases above 300 microns or there is recurrence of fluid with thickness above 300 microns, the interval is reduced by 2 weeks (+/-7 days) (to a minimum interval of 4 weeks). Designated visits will also occur at 6 months and 12 months for visual acuity, ocular examination, FA, and OCT. No treatment will occur at these visits unless the time coincides with the scheduled "treat-and-extend" visit.
- Criterion C: Rescue criteria If on subsequent follow-up visits, a
  patient loses > 15 letters with associated recurrence of fluid or
  central subfield thickness above 300 microns, the dosing interval will
  be immediately reduced to 4 weeks (+/- 7 days) for the next followup visit and for the residual duration of the study.

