# Group 2 (Treat-and-extend treatment group): End of Treatment/Month 12 (+/- 7 Days)/Early Termination visit

The following information will be collected:

- Concomitant medications
- AEs

- ETDRS visual acuity with manifest refraction
- Slit lamp examination
- Fundus examination
- Spectral Domain OCT evaluation
- Ultra-widefield fluorescein angiogram
- Pulse and blood pressure
- Weight

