# 4.5.2 Early Termination Assessments

Subjects who withdraw from the study prior to completion should return for an early termination evaluation **30** days ( $\pm$ **7** days) following the last injection/study visit for monitoring of all adverse events (serious and nonserious). The schedule of assessments for early termination is the same as that for the final visit.

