# 4.8.2 Safety Analyses

Any adverse events, laboratory assessments, physical examinations, vital signs, ocular examinations and measurements from all **30** subjects will be utilized to summarize safety data for this pilot study.

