# 5.6 PROCEDURES FOR ELICITING, RECORDING, AND REPORTING ADVERSE EVENTS

# 5.6.1 Eliciting Adverse Events

A consistent methodology for eliciting AEs at all subject evaluation timepoints should be adopted. Examples of non-directive questions include:

- "How have you felt since your last clinical visit?"
- "Have you had any new or changed health problems since you were last here?"

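### The protocol gives conflicting rules on which adverse events count for its primary endpoint: one passage filters on drug-relatedness, and the reporting period can close before Month 12

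*Protocol*

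**What the plan says.** Protocol Sections 3.3.1 and 4.8.2a make the incidence and severity of ocular and non-ocular AEs the primary outcome.

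**Which events.** Section 5 (Specification of Safety Variables) describes safety assessment as AEs and serious AEs (SAEs) judged related to ranibizumab, all deaths, and study-specific concerns. Section 5.1 defines an AE irrespective of attribution. Section 5.3 makes the investigator responsible for ensuring that "all AEs and SAEs that are observed or reported during the study, are collected and reported to the FDA", and its Assessment of Adverse Events text covers events from any source. Section 5.6.2i sends all SAEs to the manufacturer, with a separate timeline for unrelated ones, and all non-serious AEs quarterly.

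**Which period.** Section 5.3 (Adverse Event Reporting Period) starts after consent and first treatment and "ends 30 days following the last administration of study treatment or study discontinuation/termination, whichever is earlier". Section 4.5.1 and Appendix A collect AEs at Month 12 in both arms; for treat-and-extend the visit is "Group 2 (Treat-and-extend treatment group): End of Treatment/Month 12 (+/- 7 Days)/Early Termination visit". Section 4.5.2 adds an early-termination visit 30 ± 7 days "following the last injection/study visit for monitoring of all adverse events (serious and nonserious").

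**Dosing that drives the period.** Monthly subjects are last injected at Month 11. Under Section 4.3.2b, treat-and-extend intervals grow by two weeks "to a maximum interval of 12 weeks (+/- 7 days"). Of the 6- and 12-month visits it says "No treatment will occur at these visits unless the time coincides with the scheduled" treat-and-extend visit.

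**Analysis.** Section 4.8.2 uses "Any adverse events, laboratory assessments, physical examinations, vital signs, ocular examinations and measurements from all" 30 subjects, with no time limit. The SAP plans a chi-squared analysis of ophthalmic AE frequency and names neither the groups compared nor a counting period.

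**The concern.** When AEs are the primary endpoint, the rules for which events count, and over what time, should be stated once. Here two analysts could follow different passages and report different primary results, each compliant with the protocol.

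The relatedness filter matters because Section 4.2 says the study is not masked. Relatedness would be judged by an investigator who knows the regimen, so a count restricted to related events could be distorted by that knowledge.

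The period matters because its end is tied to the last injection, and the time from last injection to Month 12 depends on the arm. If a between-arm comparison used only events inside the mandatory period, the arms could be observed for different lengths of time.

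**Working it through.** **1. The filter.** The relatedness phrase in Section 5 can be read as qualifying SAEs alone, or AEs and SAEs together.
- SAEs alone: unrelated SAEs other than deaths and study-specific concerns drop out, against Sections 5.3 and 5.6.2i.
- Both: unrelated non-serious AEs drop out as well, also against Sections 3.3.1 and 5.1.

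The contradiction stands on either reading. The documents give no relatedness rate, so its size cannot be calculated.

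**2. Parsing the end rule.** It may mean the earlier of (last injection + 30 days) and discontinuation or termination. It may also mean 30 days after the earlier of last injection and discontinuation. For a subject who completes the trial, neither reading runs past last injection + 30 days.

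**3. Calendar check.** The plan states no figure to reproduce. Inputs: 30-day loading and monthly intervals, 14-day extension steps, an 84-day cap and a 30-day tail. Assumptions: nominal visit days; Month 12 on day 360 (12 × 30) or day 365; a base interval before extension of 28 or 30 days; the eye dry at every visit; first extension at the third dose (day 60) or at a Month 3 injection (day 90). The documents do not settle these.

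Period closes = last injection + 30. Shortfall = Month 12 day − closing day.

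- **Monthly:** last injection day 330; closes 330 + 30 = 360; shortfall 360 − 360 = 0, or 365 − 360 = 5.
- **Treat-and-extend from dose 3, 28-day base:** injections on days 0, 30, 60, 102, 158, 228, 312 (next due 396); closes 342; shortfall 18 or 23.
- **Treat-and-extend from dose 3, 30-day base:** injections on days 0, 30, 60, 104, 162, 234, 318 (next due 402); closes 348; shortfall 12 or 17.
- **Treat-and-extend from Month 3, 28-day base:** injections on days 0, 30, 60, 90, 132, 188, 258, 342; closes 372; no shortfall.

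Against the monthly close on day 360, the dose-3 paths close 360 − 342 = 18 or 360 − 348 = 12 days earlier. The Month 3 path closes 372 − 360 = 12 days later.

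**4. Other dry/wet sequences (28-day base).** Over the enumerated sequences, the period closes anywhere from 24 days after to 46 days before day 360 (dose-3 start), or from 26 days after to 44 days before (Month 3 start). The extremes of 46 and 44 days come from last injections on days 284 and 286, with the next due on days 368 and 370. Those visits' ±7-day windows overlap that of Month 12, so they may count as coinciding with it, and the shortfall would then disappear. Section 4.3.2b does not say what coinciding means.

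**5. Early termination.** A visit on day 23 to 37 after the last injection can fall up to 37 − 30 = 7 days outside the period. If the period ends at the subject's own discontinuation, any later visit falls outside it. The text does not say whether discontinuation means the subject (Section 4.6) or the study (Section 4.7).

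**6. Start and deaths.** The period starts after first treatment, yet Appendix A marks AE monitoring at screening, and Section 5.1 allows for events before treatment assignment. Section 5.6.2b ties death reporting to the period and cites a Section 5.1.2 that does not exist.

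**The case against.** The strongest reply is that reporting, collection and analysis are different functions. The reporting period says when events must be reported; it does not forbid collecting or analysing more. Month 12 lists AE collection and an eye examination in both arms. The example questions include "How have you felt since your last clinical visit", which reaches back across any gap. Section 4.8.2 excludes nothing by date. All of this stands, and it means that events in the gap may well be captured and analysed.

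It follows that three stronger readings fail:
- **That the reporting period contradicts the safety analysis.** It removes no treated subject, and Section 4.8.2 sets no period. The analysis period is undefined, not contradicted.
- **That treat-and-extend is systematically under-observed.** Its period can also close later than the monthly one, and many schedules leave no gap. Twelve-week intervals during the study do not close the period, because the 30 days run only from the last injection.
- **That the SAP's chi-squared result is biased.** The SAP does not say that the test is between arms.

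The reply does not remove the conflict. Section 5.3 itself requires all events during the study to be both collected and reported, and then ends mandatory reporting on a date that can precede Month 12. It also leaves the relatedness filter untouched. The specific rules elsewhere in Sections 5.1 to 5.6 make it likely that staff would capture everything, but Section 5 still says otherwise.

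**Conclusion.** The concern holds as two contradictions in the rules for the primary endpoint; severity is minor.

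The relatedness filter conflicts with the rest of the protocol on any reading. The reporting period conflicts with study-long collection, mainly in treat-and-extend. The shortfall is about 12 to 23 days for an eye always dry and extended from dose 3. It is nil on the Month 3 always-dry path and nominally 0 to 5 days in the monthly arm. These are illustrations under the stated calendar assumptions, not averages.

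A reader might go on to estimate how many subjects' events would be missed. The documents do not support that: they give no AE incidence for this population, any such figure would need an assumed share of eyes on gap schedules, and the true number is zero if Month 12 questioning captures the events. Section 3.4 already says the trial is not powered to compare severe events between the groups. The wrong section number for deaths is clerical.

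**What to change.** **Protocol, Section 5 (Specification of Safety Variables):** delete the restriction to drug-related events, and tabulate relatedness as a secondary breakdown.

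**Protocol, Section 5.3 (Adverse Event Reporting Period):** in both arms, end the period at the later of the Month 12 or early-termination visit and 30 days after the last injection. State whether discontinuation refers to the subject or the study. Reconcile the start with AE monitoring at screening in Appendix A and with Section 5.1.

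**SAP:** state that any between-arm AE comparison counts events from first injection through the Month 12 or early-termination visit in both arms, and list later events separately. The separate listing is needed because the new reporting rule can run past Month 12, for example to day 372 on the Month 3 always-dry path.

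**Protocol, Section 5.6.2b:** correct the cross-reference to Section 5.3.

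The cost is a few sentences and a few more AE records. Eyes injected at or shortly before Month 12 would need a follow-up contact: an injection on day 360 or 365 carries reporting to day 390 or 395, after the last scheduled visit. No dose, interval or treatment rule changes.

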# Assessment of Adverse Events

All AEs and SAEs whether volunteered by the subject, discovered by study personnel during questioning, or detected through physical examination, laboratory test, or other means will be reported appropriately. Each reported AE or SAE will be described by its duration (i.e., start and end dates), regulatory seriousness criteria if applicable, suspected relationship to ranibizumab (see following guidance), and actions taken.

To ensure consistency of AE and SAE causality assessments, investigators should apply the following general guideline:

#### Yes

There is a plausible temporal relationship between the onset of the AE and administration of ranibizumab, and the AE cannot be readily explained by the subject's clinical state, intercurrent illness, or concomitant therapies; and/or the AE follows a known pattern of response to ranibizumab; and/or the AE abates or resolves upon discontinuation of the ranibizumab or dose reduction and, if applicable, reappears upon re-challenge.

#### No

Evidence exists that the AE has an etiology other than from ranibizumab (e.g., preexisting medical condition, underlying disease, intercurrent illness, or concomitant medication); and/or the AE has no plausible temporal relationship to ranibizumab administration (e.g., cancer diagnosed 2 days after first dose of study drug).

Expected adverse events are those adverse events that are listed or characterized in the Package Insert or current Investigator Brochure.

Unexpected adverse events are those not listed in the Package Insert (P.I.) or current Investigator Brochure (I.B.) or not identified. This includes adverse events for which the specificity or severity is not consistent with the description in the P.I. or I.B. For example, under this definition, hepatic necrosis would be unexpected if the P.I. or I.B. only referred to elevated hepatic enzymes or hepatitis.

#### 5.4 EVALUATIONS

Reviews of body systems will be performed.

Ophthalmologic evaluations will include slitlamp examination, dilated binocular indirect high-magnification ophthalmoscopy, measurements of BCVA and intraocular pressure. Diagnostic procedures will include SDOCT and ultra-

widefield fluorescein angiography if at appropriate visit (See Section 4.5 for a detailed description of the study assessments.)

### 5.5 VITAL SIGNS

Pulse and blood pressure will be measured at protocol-specified study visits (see Section 4.5).

# 5.6 PROCEDURES FOR ELICITING, RECORDING, AND REPORTING ADVERSE EVENTS

# 5.6.1 Eliciting Adverse Events

A consistent methodology for eliciting AEs at all subject evaluation timepoints should be adopted. Examples of non-directive questions include:

- "How have you felt since your last clinical visit?"
- "Have you had any new or changed health problems since you were last here?"

# 5.6.2 Specific Instructions for Recording Adverse Events

Investigators should use correct medical terminology/concepts when reporting AEs or SAEs. Avoid colloquialisms and abbreviations.

#### a. Diagnosis vs. Signs and Symptoms

If known at the time of reporting, a diagnosis should be reported rather than individual signs and symptoms (e.g., record only liver failure or hepatitis rather than jaundice, asterixis, and elevated transaminases). However, if a constellation of signs and/or symptoms cannot be medically characterized as a single diagnosis or syndrome at the time of reporting, it is ok to report the information that is currently available. If a diagnosis is subsequently established, it should be reported as follow-up information.

# b. Deaths

All deaths that occur during the protocol-specified AE reporting period (see Section 5.1.2), regardless of attribution, will be reported to the appropriate parties. When recording a death, the event or condition that caused or contributed to the fatal outcome should be reported as the single medical concept. If the cause of death is unknown and cannot be ascertained at the time of reporting, report "Unexplained Death".

# c. Preexisting Medical Conditions

A preexisting medical condition is one that is present at the start of the study. Such conditions should be reported as medical and surgical history. A preexisting medical condition should be re-assessed throughout the trial and reported as an AE or SAE only if the frequency, severity, or character of the condition worsens during the study. When reporting such events, it is important to convey the concept that the preexisting condition has changed by including applicable descriptors (e.g., "more frequent headaches").

# d. Hospitalizations for Medical or Surgical Procedures

Any AE that results in hospitalization or prolonged hospitalization should be documented and reported as an SAE. If a subject is hospitalized to undergo a medical or surgical procedure as a result of an AE, the event responsible for the procedure, not the procedure itself, should be reported as the SAE. For example, if a subject is hospitalized to undergo coronary bypass surgery, record the heart condition that necessitated the bypass as the SAE.

Hospitalizations for the following reasons do not require reporting:

- Hospitalization or prolonged hospitalization for diagnostic or elective surgical procedures for preexisting conditions
- Hospitalization or prolonged hospitalization required to allow efficacy measurement for the study or
- Hospitalization or prolonged hospitalization for scheduled therapy of the target disease of the study.

# e. Pregnancy

If a female subject becomes pregnant while receiving investigational therapy or within 60 days after the last dose of study drug, a report should be completed and

expeditiously submitted to the Genentech, Inc. Follow-up to obtain the outcome of the pregnancy should also occur. Abortion, whether accidental, therapeutic, or spontaneous, should always be classified as serious, and expeditiously reported as an SAE. Similarly, any congenital anomaly/birth defect in a child born to a female subject exposed to the ranibizumab should be reported as an SAE.

# f. Post-Study Adverse Events

If the investigator should become aware of an SAE occurring after a subject has completed or discontinued study participating if attributed to ranibizumab exposure, including, the development of cancer or a congenital anomaly in a subsequently conceived offspring of a female subject who participated in the study, this should be reported as an SAE.

# g. Reconciliation

The Sponsor agrees to conduct reconciliation for the product. Genentech and the Sponsor will agree to the reconciliation periodicity and format, but agree at minimum to exchange monthly line listings of cases received by the other party. If discrepancies are identified, the Sponsor and Genentech will cooperate in resolving the discrepancies. The responsible individuals for each party shall handle the matter on a case-by-case basis until satisfactory resolution.

# h. AEs of Special Interest (AESIs)

AEs of Special Interest are defined as a potential safety problem, identified as a result of safety monitoring of the Product.

The ranibizumab Events of Special Interest are:

- Endophthalmitis
- Intraocular inflammation (including vitritis and uveitis)
- Cataract (Traumatic)
- Increased IOP
- ATEs including stroke
- Retinal Pigment Epithelium Tear
- Retinal Detachment

# i. SAE Reporting

Investigators must report all SAEs to Genentech within the timelines described below. The completed Medwatch/case report should be faxed immediately upon completion to Genentech Drug Safety at:

#### [contact] OR [contact]

- Relevant follow-up information should be submitted to Genentech Drug Safety as soon as it becomes available.
- Serious AE reports that are related to ranibizumab and AEs of Special Interest (regardless of causality) will be transmitted to Genentech within fifteen (15) calendar days of the Awareness Date.
- Serious AE reports that are unrelated to the ranibizumab will be transmitted to Genentech within thirty (30) calendar days of the Awareness Date.

Additional Reporting Requirements to Genentech include the following:

- Any reports of pregnancy following the start of administration with the ranibizumab will be transmitted to Genentech within thirty (30) calendar days of the Awareness Date.
- All Non-serious Adverse Events originating from the Study will be forwarded in a quarterly report to Genentech.

# 5.6.3 MedWatch 3500A Reporting Guidelines

In addition to completing appropriate patient demographic and suspect medication information, the report should include the following information within the Event Description (section 5) of the MedWatch 3500A form:

- Protocol description (and number, if assigned)
- Description of event, severity, treatment, and outcome if known
- Supportive laboratory results and diagnostics
- Investigator's assessment of the relationship of the adverse event to each investigational product and suspect medication

#### 5.6.4 Follow-up Information

Additional information may be added to a previously submitted report by any of the following methods:

- Adding to the original MedWatch 3500A report and submitting it as follow-up
- Adding supplemental summary information and submitting it as follow-up with the original MedWatch 3500A form
- Summarizing new information and faxing it with a cover letter including patient identifiers (i.e. D.O.B. initial, patient number), protocol description and number,

if assigned, brief adverse event description, and notation that additional or follow-up information is being submitted (The patient identifiers are important so that the new information is added to the correct initial report) Occasionally Genentech may contact the reporter for additional information, clarification, or current status of the patient for whom and adverse event was reported. For questions regarding SAE reporting, you may contact the Genentech Drug Safety representative noted above or the MSL assigned to the study. Relevant follow-up information should be submitted to Genentech Drug Safety as soon as it becomes available and/or upon request.

MedWatch 3500A (Mandatory Reporting) form is available at http://www.fda.gov/medwatch/getforms.html

